15.7 Appendix 7a Burden of Ostomy Care Survey (full survey, baseline and followup)

BURDEN OF OSTOMY CARE

This study aims to collect data on the burden associated with families' use of ostomy care and supplies, including ostomy-related medications, ostomy-related health care visits, travel costs to obtain ostomy-related care and supplies, and time spent on ostomy management tasks. We ask that you please answer these questions while thinking specifically about the burden of ostomy-related care. This is not a test; please give us your best estimates based on your personal experience.

1. What kind of Ostomy do you have? Colostomy Ileostomy Urostomy Other

2. In-person Visits with Wound and Ostomy Care Nurse in the past 4 weeks:

- a. Did you visit a Nurse in person in the past 4 weeks (at a medical office, hospital, and/or in your home)? No (If NO, skip to Question 3. below.) Yes
- b. **If YES:** How many times did you visit the Nurse in the past 4 weeks? 1 2 3-4 5-8 More than 8

Please answer questions 2c through 2g thinking specifically about your most recent visit to the Nurse.

- c. How much do you typically pay out-of-pocket for each Nurse visit (copayments, deductibles, or other costs for the visit that weren't covered by your insurance)?
 Nothing \$1-\$10 \$11-\$25 \$26-\$50 \$51-\$75 \$76-\$100 \$101+
- d. Did you have to travel to see the Nurse for your most recent visit? No (If NO, skip to Question 3. below.) Yes
- e. How much do you typically pay out-of-pocket to get to and from each Nurse visit (such as the cost for taxi, bus, or parking)? \$1-\$5 \$6-10 \$11-15 \$16-\$25 \$26-\$50 \$51-\$100 \$101+
- f. Approximately how far did you have to travel to the Nurse Visit location? 1-4 miles 5-8 mi. More than 8 mi.
- g. Approximately how much time did it take you to get from your home to the Nurse Visit location? 1-10 mins 11-30 mins More than 30 mins

3. Telephone and/or email consultations with a Wound and Ostomy Care Nurse in the past 4 weeks:

- a. Did you have any telephone and/or web consultations with the Nurse in the past 4 weeks? No (If NO, skip to Question 4 below.) Yes
- b. **If YES:** How many telephone and/or web consultations have you had with a Wound and Ostomy Care Nurse over the past 4 weeks? 1 2 3-4 5-8 More than 8

Please answer Question 3c thinking specifically about your most recent telephone or web consultation with the Nurse.

- c. How much did you have to pay out-of-pocket for this Nurse consultation?
 Nothing \$1-\$10 \$11-\$25 \$26-\$50 \$51-\$75 \$76-\$100 \$101+

4. In-person Visits with a Physician for stoma and/or bowel function problems in the past 4 weeks:

- a. Did you visit a Physician in person for stoma and/or bowel function problems in the past 4 weeks? No (If NO, skip to Question 5. below.) Yes
- b. **If YES:** How many times did you visit the Physician in the past 4 weeks?
 1 2 3-4 5-8 More than 8

Please answer Questions 4c through 4g thinking specifically about your most recent visit to the Physician.

- c. How much do you typically pay out-of-pocket for each Physician visit (copayments, deductibles, or other costs for the visit that weren't covered by your insurance)?
 Nothing \$1-\$10 \$11-\$25 \$26-\$50 \$51-\$75 \$76-\$100 \$101+
 - d. Did you have to travel to see the Physician for your most recent visit? No (If NO, skip to Question 5. below.) Yes
 - e. How much do you typically pay out-of-pocket to get to and from each Physician visit (such as the cost for taxi, bus, or parking)? \$1-\$5 \$6-10 \$11-15 \$16-\$25 \$26-\$50 \$51-\$100 \$101+
 - f. Approximately how far did you have to travel to the Physician visit location? 1-4 miles 5-8 mi. More than 8 mi.
 - g. Approximately how much time did it take you to get from your home to the Physician visit location? 1-10 mins 11-30 mins More than 30 mins
5. **What other sources do you use to find more information about your ostomy and daily care?** (Fill in all that apply)
 Internet Magazines Other people with an ostomy Support Group
 Other (please specify)
-
6. **If you wear a pouch and have encountered any problems with it, please explain below what those problems are/were?**
-
-
-
7. **How long was it before you felt comfortable with your daily ostomy care?**
 0 < 1 month 1-12 months 12+ months I am still not comfortable
8. **On average, how long does it take to do your daily ostomy care?**
 0-5 min 5-10 min 10-15 min 15-30 min 30-60min More than 60min
9. **Do you irrigate (flush) your ostomy?**
 Yes → Please answer 9a. I used to but stopped → Please answer 9b No Please skip to 10.
- 9a. **IF YES, How often do you irrigate your ostomy?** Once a day Every other day Every third day Other (please specify) _____
- 9b. **If you used to irrigate but stopped, why did you stop?** Pain Hernia Too time consuming
 Other (Please specify) _____
10. **Please describe the reasons you irrigate your ostomy.** (Check all that apply)
 To control timing of bowel movements To avoid blockage To avoid pain Convenience
 Other (please specify)
11. **Telephone and/or email consultations with a Physician for stoma and/or bowel function problems in the past 4 weeks:**
- a. Did you have any telephone and/or web consultations with a Physician for stoma and/or bowel function problems in the past 4 weeks? No (**IF NO**, skip to Question 12. below.) Yes
 - b. **IF YES:** How many telephone and/or web consultations have you had with a Physician over the past 4 weeks? 1 2 3-4 5-8 More than 8

Please answer Question 11c thinking specifically about your most recent telephone or web consultation with the Physician.

- c. How much did you have to pay out-of-pocket for this consultation?
 Nothing \$1-\$10 \$11-\$25 \$26-\$50 \$51-\$75 \$76-\$100 \$101+

12. Emergency Room visits for stoma and/or bowel function problems in the past 4 weeks:

- a. Did you have any visits to the Emergency Room for stoma and/or bowel function problems in the past 4 weeks? No (IF NO, skip to Question 13. below.) Yes
 b. **IF YES:** How many times did you visit the Emergency Room for stoma and/or bowel function problems in the past 4 weeks? 1 2 3-4 5-8 More than 8

Please answer Question 12c thinking specifically about your most Emergency Room visit for stoma and/or bowel function problems.

- c. How much did you pay out-of-pocket for your most recent ER visit (copayments, deductibles, or other costs for the visit that weren't covered by your insurance)?
 \$0 \$1-\$5 \$6-10 \$11-15 \$16-\$25 \$26-\$50 \$51-\$100 \$101+
 d. How much did you pay out-of-pocket to get to and from this ER visit (such as the cost for taxi, bus, or parking)? \$0 \$1-\$5 \$6-10 \$11-15 \$16-\$25 \$26-\$50 \$51-\$100 \$101+
 e. Approximately how far did you have to travel to the ER visit location? 1-4 miles 5-8 mi. More than 8 mi.
 f. Approximately how much time did it take you to get from your home to the ER visit location? 1-4 minutes 5-8 min. More than 8 min.

13. Urgent Care visits for stoma and/or bowel function problems in the past 4 weeks:

- a. Did you have any visits to an Urgent Care facility for stoma and/or bowel function problems in the past 4 weeks? No (IF NO, skip to Question 14 below.) Yes
 b. **IF YES:** How many times did you visit an Urgent Care center for stoma and/or bowel function problems in the past 4 weeks? 1 2 3-4 5-8 More than 8

Please answer questions 13c through 13f thinking specifically about your most recent Urgent Care visit for stoma and/or bowel function problems.

- c. How much did you pay out-of-pocket for your most recent Urgent Care visit (copayments, deductibles, or other costs for the visit that weren't covered by your insurance)?
 \$0 \$1-\$5 \$6-10 \$11-15 \$16-\$25 \$26-\$50 \$51-\$100 \$101+
 d. How much did you pay out-of-pocket to get to and from the Urgent Care visit (such as the cost for taxi, bus, or parking)? \$0 \$1-\$5 \$6-10 \$11-15 \$16-\$25 \$26-\$50 \$51-\$100 \$101+
 e. Approximately how far did you have to travel to the Urgent Care visit location? 1-4 miles 5-8 mi. More than 8 mi.
 f. Approximately how much time did it take you to get from your home to the Urgent Care visit location? 1-4 minutes 5-8 min. More than 8 min.

14. What type of ostomy bag system are you using? One piece Two piece

15. How many of each of the following have you used over the past 4 weeks?

- a. Wafers: 10 or less 11-20 21-30 31-50 More than 50
 b. Bags: 10 or less 11-20 21-30 31-50 More than 50

16. Medications to manage your bowel function in the past 4 weeks

- a. Have you used any medications to manage your bowel function in the past 4 weeks? (e.g., Imodium®, Metamucil®, Miralax®, Loperamide) No (IF NO, skip to Question 16. below.) Yes
- b. **IF YES:** how many different medications have you used to manage your bowel function in the past 4 weeks? ____
- c. Please list up to three medications you used most frequently to manage your bowel function and the number of days you took these medications in a typical week:
 - i. Medication _____ Number of days used (0 to 7) _____
 - ii. Medication _____ Number of days used (0 to 7) _____
 - iii. Medication _____ Number of days used (0 to 7) _____

17. Do you use the Eakin seal (moldable donut or ring)? No Yes

18. Medications to manage – treat or prevent – skin problems around your stoma in the past 4 weeks

- a. Have you used any prescription medications to manage skin problems around your stoma in the past 4 weeks? (e.g., Nystatin powder). No (IF NO, skip to Question 18. below.) Yes
- b. **IF YES:** how many different medications have you used to manage skin problems around your stoma in the past 4 weeks? None 1-2 3-4 5 or more
- c. Please list up to three medications you used most frequently to manage skin problems around your stoma and the number of days you took these medications in a typical week:
 - i. Medication _____ Number of days used (0 to 7) _____
 - ii. Medication _____ Number of days used (0 to 7) _____
 - iii. Medication _____ Number of days used (0 to 7) _____

19. How much have you spent on purchases of ostomy appliances (including wafers and bags in total over the past 4 weeks)? \$0 \$1-\$25 \$26-50 \$51-100 \$100-\$150 \$150-\$200 \$200-\$250 over \$250

20. About how many times a day do you empty your drainable ostomy bag (or discard your closed/disposable bag)?

- None 1-4 5-8 More than 8

21. Over the past 4 weeks, what was the highest number of bag emptyings in a 24-hour period?

- None 1-4 5-8 More than 8

22. Over the past 4 weeks, what was the lowest number of bag emptyings in a 24-hour period?

- None 1-4 5-8 More than 8

23. How often do you typically discard a used bag and use a new bag?

- At every emptying Once a day Once every 2-3 days Less often

24. How much time does it usually take you to empty/dispose your bag?

- 1-5 minutes 5-10 minutes 10-15 minutes More than 15 minutes

25. How often do you typically change your wafer on a typical week? 1 2 3 4-7 More than 7

26. How much time does it usually take you to change your wafer and bag?

- 1-15 minutes 16-30 minutes 30-45 minutes 45-60 minutes More than 60 minutes

27. Do you usually receive help caring for your stoma and changing your ostomy appliance?

- a. No (skip to Question 27 below)
- b. Yes IF Yes, please check who your helper(s) is(are):
 Spouse/Significant Other Other family member Friend Home care nurse Other Paid Caregiver Other (please specify) _____

28. Has your bag leaked at any time over the past 4 weeks?

- a. No (skip to Question 28 below)
- b. Yes **IF YES**, how many times? 1-4 5-8 More than 8
- c. How many of these times involved a full spillage of your bag contents? 1-4 5-8
More than 8
- d. How much time does it require to clean up after a bag leak or spill? 1-30 minutes 31-60 mins.
More than 60 mins

29. Do you have waterproof covers on your mattress and primary chair(s)?

- a. No → Skip to Question 29 below.
- b. Yes **IF YES**, how much did you spend to purchase them?
\$0 \$1-\$10 \$11-\$25 \$26-\$50 \$51-\$75 \$76-\$100 \$101-\$150 \$151+

30. Do you have to make alterations to your clothing to accommodate your ostomy appliance?

- a. No **IF NO**, skip to Question 30 below.
- b. Yes **IF YES**, do you make these modifications yourself?
 - i. No
 - ii. Yes → **IF YES**, How much do you spend for these modifications?
\$0 \$1-\$5 \$6-\$10 \$11-\$15 \$16-\$25 \$26-\$50 \$51-\$100 \$101+

31. Do you make some or all your own clothes because you have an ostomy and nothing in the clothing stores will fit you appropriately?

- a. No → **IF NO**, skip to Question 32 below.
- b. Yes → **IF YES**, how much do you spend to make your own clothes in a year?
\$0 \$1-\$5 \$6-\$10 \$11-\$15 \$16-\$25 \$26-\$50 \$51-\$100 \$101+

32. Did you purchase any fashion accessories specifically made for someone with an Ostomy (for example, fashion wraps, special underwear, Stealth belt)?

- a. No → **IF NO**, skip to Question 33 below.
- b. Yes → **IF YES**, how much did you spend to purchase your special underwear/girdle/body wrap?
\$0 \$1-\$5 \$6-\$10 \$11-\$15 \$16-\$25 \$26-\$50 \$51-\$100 \$101+

33. Do you wear a hernia belt?

- a. No → **IF NO**, skip to Question 34 below.
- b. Yes → **IF YES**, how much did you spend to purchase your hernia belt(s)?
\$0 \$1-\$5 \$6-\$10 \$11-\$15 \$16-\$25 \$26-\$50 \$51-\$100 \$101+

34. How would you describe your current employment?

(Please select only one)

- Full time
- Part time
- Retired and not working another job
- Home maker
- Temporarily laid off
- Unemployed and looking for work
- Unemployed and **not** looking for work
- On disability

Other: (please explain) _____

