5.0 ELIGIBILITY CRITERIA

5.1 Eligibility criteria

1. Cancer survivors over 21 years of age having undergone a procedure that needed an intestinal stoma (fecal or urinary). Survivors with temporary ostomies will be included.
2. All participants must have a full understanding of the protocol and be able to sign an informed consent form.
3. Having an identified caregiver is **not** a requirement for eligibility.
4. All participants will attend their first training session at least six weeks after their operation.
5. There is no maximum time since surgery.

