6.0 STRATIFICATION FACTORS

Potential stratification factors are gender, medical center site, and fecal vs. urinary ostomy. Gender and site will be stratified in the randomization process, whereas ostomy type will be explored in the analysis.

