**Statistical Analysis Plan**

## Statistical Analysis Plan

**General.** Aim 1 will be analyzed with linear mixed models for repeated measures. Aim 2 will utilize a variety of sources and methods to enumerate the intervention program and ostomy-related family resources in each study arm.

**Aim 1:** Using our enhanced telehealth techniques, determine if **patient activation**, self-efficacy, ostomy-related knowledge, and HRQOL will be improved and sustained over time in the online interactive communication Ostomy Self-Management Telehealth program (OSMT) curriculum compared to a UC group.

Under an intent-to-treat approach, change in outcomes will be evaluated longitudinally with linear mixed models, testing the effect of study arm adjusted for potential confounders. Such models evaluate both associations and rates of change, accounting for within-subject correlation. The Primary Outcome will be PAM. Secondary Outcomes include SE, COH-QOL-CRC scales, and Ostomy Knowledge. Post hoc contrasts will evaluate effect of training (baseline to post) and whether effect is sustained after training (6 month post to follow-up). Standard multivariable modeling procedures will be used to select or eliminate potential confounding variables, starting with candidate variables that are biologically plausible or found to be associated with endpoint change scores (baseline vs. follow-up) in bivariate analyses with a p-value of less than 0.20. Potential candidate covariates and confounders include (but are not limited to) CG participation in training sessions, depression (HADS), time since surgery, ostomy type, age, sex, stage, anticipated permanence of ostomy, and pre- or post-surgical radiation or chemotherapy. We will explore potential interaction for plausible effect modifiers, such as gender, or having a CG.

The COH QOL-CRC assesses ostomy burden and care abilities, including time taken to perform daily ostomy care, comfort with ostomy care, comfort with diet, adjustment of diet for ostomy, appetite, clothing and other problems with ostomy placement. We will also measure clinically related outcomes, including medical attention for problems with bowel, bladder, or ostomy. Changes in these responses will be compared between treatment groups with linear mixed models, chi-square tests or t-tests, as appropriate.

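### The physician, emergency and urgent-care items do not ask about urinary problems, although urostomy patients are eligible and the plan names bladder problems as part of a measured outcome

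*Protocol*

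**What the plan says.** Protocol 5.1 admits survivors "having undergone a procedure that needed an intestinal stoma (fecal or urinary"), and 7.2.1.2 lists a urology clinic among the recruitment sources at one site. Item 1 of the full Burden of Ostomy Care survey (Appendix 7a) reads "What kind of Ostomy do you have? Colostomy Ileostomy Urostomy Other", so the form is meant for urostomy participants too.

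The SAP, in the same words as Protocol 12.2, says the study will measure clinically related outcomes, "including medical attention for problems with bowel, bladder, or ostomy". For Aim 2, Protocol 12.4 counts ostomy-related physician and emergency encounters and does not limit them by organ.

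The items that record those contacts are limited:

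- 7a item 4 and 7b item 3: "In-person Visits with a Physician for stoma and/or bowel function problems in the past 4 weeks"
- 7a item 11: "Telephone and/or email consultations with a Physician for stoma and/or bowel function problems in the past 4 weeks"
- 7a item 12: "Emergency Room visits for stoma and/or bowel function problems in the past 4 weeks"
- 7a item 13 (urgent care): the same restriction.

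The restriction is repeated in the yes/no question under each heading. Nurse contacts (7a items 2 and 3, 7b items 1 and 2) carry no restriction by type of problem. On ostomy type, section 6.0 says: "Gender and site will be stratified in the randomization process, whereas ostomy type will be explored in the analysis".

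**The concern.** A urostomy participant who sees a physician or goes to an emergency room for a urinary problem, and who reads the question literally, answers No. The visit is then not counted. The sub-items on out-of-pocket payment and, for visits, travel are skipped with it, so the financial-burden data for Question 2.1 lose the same events.

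The study's own material treats such contacts as part of living with a urostomy: item 8 of the knowledge survey (Appendix 6) includes, among its answer options, bleeding and absent urine as reasons to contact a urologist or go to the emergency room.

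At stake is a stated outcome with no visible data source for one of its parts, and a comparison by ostomy type in which one group's recorded use is low partly because of the form. The primary outcome (PAM) is not affected.

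**Working it through.** **Planned outcome against instrument.** The plan gives no figure for this outcome, so there is nothing to reproduce. The check is a comparison of texts.

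| Category of problem | 12.2 and SAP | Physician, emergency and urgent-care items | Nurse items |
|---|---|---|---|
| Stoma or ostomy | named | asked | counted, any problem |
| Bowel | named | asked | counted, any problem |
| Bladder or urinary | named | not asked | counted, any problem |

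Could another form fill the gap? Appendix 2a has no question on medical attention for urinary problems. Appendix 2b consists of 0-10 scaled items, which do not count contacts. Appendix 7b has no emergency or urgent-care item at all. No source for the urinary part is visible.

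**Illustrative size.** The documents give neither the urostomy share nor the reasons for contact, so both inputs are assumptions:

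- u = share of participants with a urostomy
- q = share of their physician, emergency and urgent-care contacts that are urinary and neither stoma nor bowel problems, all answered No.

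With equal contact rates across ostomy types, the share of all such contacts missed is u × q:

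- u = 0.20, q = 0.25: 0.20 × 0.25 = 5%
- u = 0.40, q = 0.50: 0.40 × 0.50 = 20%
- wider inputs, u = 0.10-0.40 and q = 0.20-0.60: 2% to 24%.

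If urostomy participants have twice the contact rate, the share is 2uq/(1 + u). The wider inputs then give 2 × 0.10 × 0.20/1.10 = 3.6% to 2 × 0.40 × 0.60/1.40 = 34.3%. Within the urostomy group the missed share is q itself. If respondents report urinary visits anyway, q falls towards zero.

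**Arm comparison.** Both arms receive the same form. With equal true use, equal contact rates across types and the same urostomy share in each arm, both record the fraction 1 − uq and no difference is created. A difference needs unequal shares. Suppose 35% in one arm and 25% in the other:

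- q = 0.50: (1 − 0.35 × 0.50)/(1 − 0.25 × 0.50) = 0.825/0.875 = 0.943, about 6%
- q = 0.25: (1 − 0.35 × 0.25)/(1 − 0.25 × 0.25) = 0.9125/0.9375 = 0.973, under 3%.

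How likely is such a gap? Assume an overall share of 30% and ignore stratification. The standard error of the difference in shares is √(2 × 0.30 × 0.70/n): 0.0748 at 75 per arm and 0.0592 at 120 per arm. A gap of at least 10 points in either direction then has probability of about 18% and 9% (normal approximation).

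**The case against.** **Whose bladder?** The curriculum describes a urostomy as made when the bladder has been removed, so the bladder wording could refer to participants with fecal stomas. This stands as a limit: the loss cannot be said to fall on one ostomy type only. It does not remove the gap, because under either reading no visible item asks.

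**Two aims.** The bladder wording belongs to the Aim 1 paragraph. Hypothesis 2.2 concerns ostomy-specific services, and the medications listed in 12.4 are for bowel and skin only. A reader might infer that Hypothesis 2.2 is contradicted by its own form. The documents do not support that, because they do not settle whether, say, a urinary infection counts as ostomy-specific. What can be said is that 12.4 is worded more broadly than the items.

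**Literal reading.** The survey introduction speaks of ostomy-related care in general, and a urostomy drains through the stoma, so some respondents will report urinary visits as stoma problems. This stands too. The loss is probably partial, and uneven between respondents. A reader might also infer that the survey cannot show any effect of the intervention in urostomy participants. That goes too far, since their stoma problems and all nurse contacts are recorded.

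**Bias between arms.** A reader might infer that the wording produces a false arm difference. It does so only if chance leaves ostomy type unbalanced, which is sampling variation and not systematic bias. The full form is also given at baseline, and ostomy type is recorded and is a candidate covariate for Aim 1. Sections 12.3 to 12.7 state no such adjustment for Aim 2.

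**Completeness of the text.** Appendix 7a as shown ends at item 34, without the open question that 8.2 places in it, and 12.7 and 12.12 cite an Appendix D. Another urinary item cannot be ruled out entirely. The affected items themselves are fully visible.

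**Conclusion.** The mismatch is real: 12.2 and the SAP name a category of medical attention that the physician, emergency and urgent-care items do not ask about, in a trial that enrols urostomy patients. The consequence is mainly under-ascertainment, with distorted comparison by ostomy type. Absolute differences also shrink: if 20% of contacts go unrecorded and any effect is proportional, the recorded difference is 80% of the true one.

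The size is not known. The 5-20% range rests on an assumed urostomy share and an assumed mix of reasons, equal contact rates across types, and literal answering; the true figure could be close to zero or, with higher contact rates, above that range. The 3% to 6% arm differences require an assumed 10-point imbalance with no adjustment. The point deserves correction because it leaves part of a stated secondary outcome unmeasured and is cheap to put right.

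**What to change.** 1. For participants not yet at baseline, word 7a items 4, 11, 12 and 13 and 7b item 3 as *stoma, bowel and/or urinary problems*, in both headings and sub-items.
2. For participants already enrolled, keep the present items and add a separate question on urinary contacts, asking only for contacts not already reported. Rewording their items between baseline and follow-up would make a change of wording look like increased use.
3. Report these outcomes by ostomy type, or adjust for it, and state this for Aim 2.
4. Where urinary contacts were not asked, say so, and either remove bladder from the measured outcome in 12.2 and the SAP or name another source for it.

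The cost is one phrase in five items, one added question and a form-version flag. The flag identifies who answered which wording but does not make the two comparable. Participants given the added question will have no baseline value for it, so their urinary contacts should be reported separately from change from baseline. If data collection is finished, only steps 3 and 4 apply, and they need no new data.
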